As this is the first use of talimogene laherparepvec with pembrolizumab, the phase 1b study is necessary to evaluate the safety of talimogene laherparepvec in combination with pembrolizumab. In addition, the phase 1b part of the study will evaluate potential blood and [REDACTED] that associate with response or resistance to talimogene laherparepvec in combination with pembrolizumab. During phase 1b, talimogene laherparepvec will be started 5 weeks preceding pembrolizumab administration and continuing during pembrolizumab administration. This dosing schedule will allow for correlative [REDACTED] studies to be performed before and after talimogene laherparepvec is combined with pembrolizumab.

An analysis of the phase 1b portion of the study was recently completed ([Ribas et al, 2017](#)). Twenty one patients with advanced melanoma were treated with talimogene laherparepvec followed by pembrolizumab. Median follow-up was 18.6 (17.7 to 20.8) months. Therapy was generally well tolerated. No dose-limiting toxicities occurred. The most frequent adverse events were fatigue (62%), fever (43%), chills (48%), and rash (33%). One event of grade 1 cytokine-release syndrome was described as possibly related to the combination. The other serious adverse events were attributed solely to pembrolizumab and included grade 3 autoimmune hepatitis, grade 3 aseptic meningitis and grade 4 pneumonitis (one patient each). The confirmed objective response rate (ORR) was 62% with a complete response (CR) rate of 33% per immune-related response criteria. Responses occurred across all substages of melanoma. Median PFS and OS were not reached at the time of last follow-up. Response to the combination therapy did not appear to be associated with baseline CD8+ T cell infiltration or IFN-gamma signature. Patients who responded to the combination therapy had increased CD8+ T cells, elevated PD-L1 protein expression as well as IFN-gamma gene expression on several cell subsets in the tumors after

Approved

talimogene laherparepvec treatment. These findings suggest that talimogene laherparepvec may improve the efficacy of pembrolizumab by changing the tumor microenvironment.

In both phases of the study, pembrolizumab will be administered at a fixed dose of 200 mg either every 2 weeks in phase 1 or every 3 weeks in phase 3. A 2 mg/kg Q3W dose is approved for metastatic melanoma in some countries.

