Subjects with BRAF^{V600} mutant melanoma or unknown BRAF^{V600} mutation status who have not received a BRAF inhibitor are also eligible for the phase 3 of this study as first-line treatment if they meet the following criteria: lactate dehydrogenase (LDH) $<$ ULN, no clinically significant tumor related symptoms, and absence of rapidly progressing metastatic melanoma.

Note: Subjects (BRAF mutant, wildtype and UNK) who received prior adjuvant therapy for melanoma will not be excluded (including, but not limited to radiotherapy, interferon, limb infusion/perfusion, ipilimumab, or use of investigational agents in the adjuvant setting). However, the subject must have ended therapy at least 28 days prior to enrollment. No prior anti-CD137, ipilimumab or other CTLA-4 inhibitor, talimogene laherparepvec, tumor vaccine, or any other oncolytic viruses or drugs specifically targeting T-cell co-stimulation or checkpoint pathways are allowed in a non-adjuvant setting. No prior pembrolizumab or any other inhibitor of PD-1, PD-L1, or PD-L2 are allowed in any setting.

106 Measurable disease defined as:

- at least 1 visceral or nodal/soft tissue melanoma lesion that can be accurately and serially measured in at least 1 dimension and for which the longest diameter is ≥ 10 mm as measured by CT scan or MRI. Lymph nodes must measure ≥ 15 mm in their short axis to be considered measurable by CT scan or MRI

111 Subject has a tumor sample (archival sample obtained within 3 months prior to day 1 and no systemic therapy given 3 months prior to archival biopsy or newly obtained biopsy) that is submitted for PD-L1 assessment prior to randomization. Subject must submit the tumor sample during screening for PD-L1 expression testing at a central laboratory. Subjects will be eligible to participate regardless of the level of PD-L1 expression. Subjects with an unevaluable archival sample for PD-L1 expression testing and BRAF^{V600} mutation testing may obtain a new biopsy and subjects with an unevaluable newly obtained biopsy may undergo re-biopsy at the discretion of the investigator. If repeat sample is also unevaluable and the subject is otherwise eligible, the investigator may enroll the subject with or without a second re-biopsy. Subjects with an unevaluable newly obtained biopsy may undergo re-biopsy at the discretion of the investigator. If

the subject is ready to be randomized and treated after re-biopsy, randomization and start of treatment may proceed.

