10.5.2 Primary Endpoint

10.5.2.1 Phase 1b

Subject incidence of DLT: The subject incidence of DLT will be summarized using the DLT analysis set.

10.5.2.2 Phase 3

The primary analyses of the primary endpoints of PFS and OS will be based on stratified log-rank tests as a primary method for testing the null hypothesis of no treatment difference.

The stratification factors will include randomization factors per IVRS and PD-L1 status at baseline (positive vs not positive). Inclusion of PD-L1 is considered in the stratified analysis because PD-L1 overexpression could be a potential prognostic factor, and its pretreatment status may not be able to be confirmed prior for use as a stratification factor at the time of randomization. In order to allow for the use of PD-L1 status in a stratified analysis, indeterminate and missing PD-L1 status will be classified together with the “negative” PD-L1 group. Hazard ratios will be estimated using Cox proportional hazards (PH) models stratified by randomization factors per IVRS and the baseline

PD-L1 status (positive vs not positive). Kaplan-Meier (KM) time to event curves will be presented by the randomized treatment group.

Statistical testing of a treatment effect for PFS and OS will follow the multiple hypothesis testing procedure as described in [Section 10.5](#).

Subgroups and covariates for analyses of PFS and OS will include, but not limited to, disease stage (IIIB/C to IVM1a, IVM1b/c), known PD-L1 status (positive, negative) and prior treatment with BRAF inhibitor.

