Baseline in general refers to study day 1. The baseline value of a parameter (eg, vital signs, laboratory tests, and tumor measurement) is considered to be the latest value prior to receiving any study drug (ie, on or prior to the first date of dosing) in the respective phase of the study. If the measurement is done on the same day as the first dose of any study drug and the exact measurement time relative to the first dose of any study drug is unknown, it will be assumed that the measurement is done before the administration of the first dose of any study drug. If a subject does not receive any study drug, baseline is the closest recorded measurement on or before the

enrollment/randomization date. *BRAF* mutational status, which is not sensitive to treatment, will be considered baseline regardless of the timing of ascertainment. For phase 1b, talimogene laherparepvec starts 5 weeks before pembrolizumab, therefore Week -5 is used as baseline. [REDACTED]

Best overall response (BOR) per modified irRC (Phase 1b)

BOR of complete response (CR), partial response (PR), stable disease (SD), progressive disease (PD) or unevaluable (UE) will be derived based on investigator assessment per modified irRC. Overall visit response assessments occurring **on or** after the start of the first subsequent anticancer therapy, including complete or partial removal/reduction of any index lesion which contained melanoma on pathology evaluation or pathology results were unknown, will not be included. **The timepoint responses after initial confirmation of PD will not be used to derive BOR.**

Confirmation of CR, PR, and PD is required as noted in the individual definitions for CR, PR and PD per modified irRC (refer to protocol Appendix D). For the derivation of BOR, the overall visit response will be considered SD if it is an unconfirmed CR or PR, and UE if it is either SD earlier than 84 days after the date of enrollment or an unconfirmed PD when confirmation of PD is required (ie, initial PD without clinical instability). As indicated in [Table 1](#), BOR is defined as the best overall visit response in the following order: CR, PR, SD, PD, or UE.

Table 1. Matrix of Determining BOR per Modified irRC

Visit Overall Response Sequence	Examples	Best Overall Response	Specifications

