10.1 General Principles

In general, the efficacy and safety analyses will be conducted separately for phase 1b and phase 3. Data collected after the analysis data cutoff date at each analysis time will be excluded.

For phase 1b, descriptive statistics for the confirmed ORR, BOR, DCR, DRR, DOR, PFS, and OS will be provided where tumor response evaluations are based on investigator assessments using modified irRC. The analysis will include data from phase 1b subjects in the Safety Analysis Set.

For phase 3, the efficacy analyses will be conducted on the Full Analysis Set. Treatment effects on efficacy endpoints will be evaluated and compared between the 2 treatment arms according to the treatment as randomized. Formal treatment comparisons will be performed on the dual primary endpoints and the 3 key secondary endpoints.

Mean, standard deviation, median, first and third quartiles, minimum and maximum will be calculated for continuous variables; frequency count and percent will be calculated for binary and categorical variables. For binary endpoints, proportions and the corresponding 95% confidence intervals, and p-values will be based on normal approximations and the treatment comparison (ratio of proportions, treatment over control) will be based on Cochran-Mantel-Haenszel test (see code fragment in [Appendix C](#)) stratified by randomization stratification factors and baseline PD-L1 status as the primary method. Additionally, p-values from the stratified Mantel-Haenszel test for the common risk difference will also be calculated (see code fragment in [Appendix C](#)). Exact confidence intervals (Clopper & Pearson 1934) (see code fragment in [Appendix C](#)) and Fisher exact tests (see code fragment in [Appendix C](#)) for binary endpoints will be considered for phase 1b and all subgroup analyses in phase 3. Logistic regression will be used to estimate the odds ratio, 95% CI for the odds ratio, and p-value (see code fragment in [Appendix C](#)).

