██ time-to-event endpoints will be analyzed as follows. Time to-event endpoints will be summarized descriptively by treatment group using the Kaplan-Meier (K-M) method. Standard errors of estimated treatment differences by time point will be calculated using Greenwood's formula (Kalbfleisch and Prentice, 1980). KM median estimates will be provided for each treatment arm along with KM estimates at appropriate times for each endpoint (eg, month 3, month 6, month 9, month 12, etc for PFS and 1 year, 2 year, 3 year etc. for OS). In addition, the point estimate of the adjusted risk difference (difference in Kaplan-Meier estimates at the time point of interest, treatment arm – control arm) and the corresponding 95% confidence interval will be provided using the inverse variance-weighted method (see code fragment in [Appendix C](#)). Stratified log-rank test statistics and associated p-values will also be used as the primary analysis method to assess the hypothesis of no treatment difference. Hazard ratios will be estimated using stratified Cox proportional hazards (PH) models (see code fragment in [Appendix C](#)).

For stratified analyses, the stratification factors will include randomization stratification factors per IVRS and PD-L1 status at baseline (positive vs not positive). The criteria for PD-L1 status is as follows:

- Any available PD-L1 positive result makes the subject a positive (irrespective of tissue analyzed and irrespective of the timing).
- If there are more than one PD-L1 result, and none of them are positive, then choose the one from a fresh biopsy.

Listings (eg, baseline characteristics, adverse events and exposure) of subjects in the Retreatment Analysis Set will be provided.

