10.5.3 Analyses of Exploratory Endpoints

10.5.3.1 PD-L1 Induction

[figure not shown]
PD-L1 expression from tumor biopsy tissue samples will be reported as positive or negative. PD-L1 induction (ie, change of PD-L1 expression from negative to positive from paired biopsy samples taken before and after initiating talimogene laherparepvec)

will be tabulated overall and for injected and uninjected lesions. The pairing will be based on lesion number. Should there be multiple biopsies on the same lesion after initiating talimogene laherparepvec, and if there is any positive observation, the post-dose observation for PD-L1 will be considered positive. The analysis will include subjects in the PD-L1 Negative Analysis Set in the Safety Set of **Phase 1b**.

10.5.3.3 iORR, iBOR, iDRR, iDOR, iPFS (response evaluation by investigator using modified irRC-RECIST)

These endpoints will be analyzed in the similar manner to corresponding primary and secondary endpoints assessed by BICR.

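### The rule that assigns the baseline PD-L1 stratum in the primary PFS and OS tests accepts positive results from any time, including after dosing

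*SAP*

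**What the plan says.** SAP 10.1 lists the factors for all stratified analyses as the IVRS randomization factors plus baseline PD-L1 status (positive or not positive). Its first criterion for that status is "Any available PD-L1 positive result makes the subject a positive (irrespective of tissue analyzed and irrespective of the timing". Its second covers subjects with several results and none positive: the fresh biopsy is used, again with no time limit.

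The factor enters the stratified log-rank tests and Cox models for PFS and OS (SAP 10.5.1.1; Protocol 10.5.2.2). It also enters iPFS and the OS subgroup, which follow the PFS analysis (SAP 10.5.1.2), and the Cochran-Mantel-Haenszel test used for iCRR, which is "stratified by randomization stratification factors and baseline PD-L1 status as the primary method" (SAP 10.1).

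Other passages on timing:

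- SAP Section 6, Baseline: the baseline value of a parameter "is considered to be the latest value prior to receiving any study drug". The only visible timing exemption is for BRAF: "mutational status, which is not sensitive to treatment, will be considered baseline regardless of the timing of ascertainment".
- SAP 7.4 and 7.5: the phase 3 PD-L1 negative and positive sets are defined by status before randomization.
- Protocol 10.5.2.2: PD-L1 is added in the analysis because "its pretreatment status may not be able to be confirmed prior for use as a stratification factor at the time of randomization".

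**The concern.** Section 6 exempts BRAF from the timing rule because treatment does not change it. That reason does not carry over to PD-L1. Protocol 2.4 reports that phase 1b responders showed "elevated PD-L1 protein expression as well as IFN-gamma gene expression on several cell subsets in the tumors after" T-VEC. SAP 10.5.3.1 plans a phase 1b analysis of exactly this "change of PD-L1 expression from negative to positive from paired biopsy samples taken before and after initiating talimogene laherparepvec".

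A programmer who follows SAP 10.1 literally would count a week 5 positive as a baseline positive. If T-VEC converts more subjects than placebo does, both primary tests are stratified on a variable that treatment has changed. Converted subjects then sit in the positive stratum of the T-VEC arm, and like is no longer compared with like.

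With a favourable marker this pushes the hazard ratio against T-VEC and costs power. With an adverse marker it pushes the hazard ratio towards T-VEC and inflates false positives. The protocol says only that PD-L1 could be prognostic, so the direction is not known in advance.

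**Working it through.** **Plan figures reproduced.** Events = 4(z₁₋α/₂ + z₁₋β)² / (ln HR)².

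- PFS, HR 2/3, 2-sided 0.005, 90% power: 4(2.807 + 1.282)² / 0.4055² = 407, as stated. With the printed HR of 0.67, power at 407 events is 89.1%.
- OS, using the Protocol Table 12 nominal levels at 252/282/315/346 deaths: overall alpha 0.0450 and power 89.6% (stated: 0.045 and 90%).
- Final OS look alone (346 deaths, HR 0.70, 2-sided 0.0336, so 1.68% per direction): √346/2 × 0.3567 − 2.125 = 1.19, which is 88.3% power.

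**Assumptions not in the documents.** 50% positive at baseline. At week 5, 20% or 40% of not-positive subjects convert on T-VEC and 10% on placebo. Marker hazard ratio (positive vs not positive) 0.6 to 1.67.

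**Hand check of direction.** Take no treatment effect, hazard 1 in subjects not positive at baseline, and ignore events before week 5. For marker HR 0.6, the mean starting hazard in the recorded positive stratum is:

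- placebo, 10% converting: (0.50×0.6 + 0.05)/0.55 = 0.636
- T-VEC, 20% converting: (0.30 + 0.10)/0.60 = 0.667, a ratio to placebo of 1.05
- T-VEC, 40% converting: (0.30 + 0.20)/0.70 = 0.714, a ratio of 1.12

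For marker HR 1.67 the same sums give ratios of 0.97 and 0.92. Random conversion leaves the not-positive stratum near 1, so the stratified hazard ratio should fall between 1 and these values.

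**Simulation.** 10,000 replicates per scenario; 692 subjects (SAP Table 5), 1:1. Control curves come from the notes to Protocol Figures 1 and 2. Accrual runs over 26 months with half enrolled at two thirds of the period; loss is 5% a year (OS) or 10% (PFS). True HR is 0.70 (OS), 0.67 (PFS) or 1. Conversion is random at day 35 among subjects still event-free and in follow-up. Each data set is analysed with true baseline strata and then with any-time strata (shown as baseline → any-time).

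Final OS test:

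| Marker HR | Conversion, T-VEC/placebo | HR under null, any-time | Power | False rejections (nominal 1.68%) |
|---|---|---|---|---|
| all | 10%/10% | 0.998–1.002 | 87.9–88.5% → 87.8–88.1% | 1.6–1.9% per direction |
| 0.6 | 20%/10% | 1.022 | 88.6% → 83.5% | against T-VEC 1.9% → 3.1% |
| 0.6 | 40%/10% | 1.067 | 88.1% → 69.2% | against T-VEC 1.5% → 6.1% |
| 0.8 | 20%/10% | 1.009 | 88.5% → 86.2% | against T-VEC 1.8% → 2.3% |
| 0.8 | 40%/10% | 1.031 | 88.3% → 80.7% | against T-VEC 1.7% → 3.3% |
| 1.0 | 40%/10% | – | 88.4% → 87.0% | – |
| 1.25 | 20%/10% | 0.989 | – | for T-VEC 1.8% → 2.1% |
| 1.25 | 40%/10% | 0.977 | – | for T-VEC 1.7% → 2.9% |
| 1.67 | 20%/10% | 0.978 | – | for T-VEC 1.8% → 2.9% |
| 1.67 | 40%/10% | 0.940 | – | for T-VEC 1.7% → 5.9% |

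PFS test (407 events, 2-sided 0.005), at 20% and 40% conversion:

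- Marker HR 0.6: power 88.5% → 83.2% and 89.1% → 69.2%.
- Marker HR 1.67: false positives for T-VEC 0.27% → 0.54% and 0.18% → 1.43% (nominal 0.25%).

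Monte Carlo standard errors are 0.3–0.5 points for power, 0.1–0.24 for OS false rejections and about 0.05–0.12 for PFS false rejections. Interim OS looks are not modelled.

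**Sensitivity.**

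- Adding the two IVRS factors (8 strata, 4,000 replicates; assumed 50% advanced stage with HR 1.7, 10% prior BRAF inhibitor with HR 1.3), marker 0.6: OS power 87.2% → 82.1% and 86.9% → 68.6%.
- A separate simulation used 660 subjects, 60% positive, marker HR 0.5–0.8, exponential times, conversion on T-VEC only, and one OS look at 2-sided 0.045. OS power fell from about 91% to 80–87% at 20% conversion and to 61–83% at 40%. There was no bias with pre-dose results only (HR 0.998) or with equal 20% conversion (HR 0.999–1.001).

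**The case against.** The strongest reply is that the authors meant only screening samples. Screening can yield archival, fresh and repeat biopsies, and treatment may start after a re-biopsy without waiting for its result (Protocol 7.2.1). On that reading, timing means sample age or report date, and the factor is called baseline throughout. This is plausible, but the criterion does not say it, and report date is not collection date.

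Second, no trigger is visible. Protocol criterion 111 says: "Subject must submit the tumor sample during screening for PD-L1 expression testing at a central laboratory". PD-L1 induction is a phase 1b analysis only. Part of the Section 6 baseline definition is redacted and may hold a PD-L1 rule. All of this stands, and it is why the finding is conditional. However, phase 3 tissue is also taken at week 5 (Protocol 6.2.1.1), and Protocol 7.5 allows collected tumor samples to be used for any test in the protocol. Post-dose PD-L1 results are therefore permitted, though not shown to exist.

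Third, the inputs are assumed, and the conversion rates imply complete week 5 testing. With half coverage and marker HR 0.6, 20%/10% becomes 10%/5% (power 88.6% → 86.1%) and 40%/10% becomes 20%/5% (86.9% → 78.5%). The effect shrinks but remains. Conversion was also taken as random, whereas the phase 1b observation concerns responders and does not establish a change from negative to positive status.

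Fourth, the hypotheses are of improvement, so rejections against T-VEC would not produce a false claim of benefit. That is right. With a favourable marker the main cost is power; inflation in favour of T-VEC needs an adverse marker, and nothing in the documents points to one.

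**Conclusion.** The concern holds. The criterion in SAP 10.1 contradicts the pre-dose baseline in Section 6 as far as that text is visible, the pre-randomization PD-L1 sets in 7.4 and 7.5, and the protocol's stated purpose for the factor. It governs both primary tests and three key secondary tests.

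The harm is conditional. If no post-dose phase 3 PD-L1 results exist, or conversion is equal in the two arms, the treatment comparison does not shift. Otherwise the effect ranges from about 2 points of OS power (marker 0.8, 20% vs 10%) to about 19 points (marker 0.6, 40% vs 10%). With an adverse marker, false positives for T-VEC at the final OS look reach up to 5.9% against a nominal 1.68%. Prevalence, prognostic strength and conversion rates are all assumed.

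It should be fixed. Confidence is medium, because the documents do not show whether week 5 tissue is assayed for PD-L1.

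**What to change.** Before unblinding, replace the first criterion in SAP 10.1 with wording such as: *Count a subject as PD-L1 positive if any tissue sample collected before the first dose of study drug (or, in subjects never dosed, on or before randomization) tests positive, whichever sample it is and whenever the laboratory reports it.* Put the same collection window on the second criterion. State that, within this window, the rule takes precedence over the latest-value rule in Section 6. Class subjects with only post-dose results as not positive, and keep later results for exploratory analyses.

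The PD-L1 sets in SAP 7.4 and 7.5 use randomization as the limit, while treatment may start up to 5 days later (Protocol 5.1). Align them in the same edit.

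The cost is a few lines of SAP text. No new data are needed, and event goals and alpha do not change. Multiple and late-reported screening samples still count, and subjects without a pre-dose result are handled as SAP 10.5.1.1 already handles missing status. If no post-dose results exist, no subject changes stratum.

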10.2 Subject Accountability

The number of subjects enrolled will be tabulated by country and investigator site overall and by treatment group (when applicable). Subject disposition (including the number enrolled, treated, ended treatment, ended radiographic follow-up and that completed the safety follow-up visit and the study) will be summarized separately for all enrolled subjects in phase 1b, and phase 3. Subject accountability will be tabulated by respective treatment group when applicable. Reasons for not receiving treatment, for ending treatment, ending radiographic follow-up and not completing the 30-day safety follow-up visit will be provided.

Key study dates for the first subject enrolled, last subject enrolled, first subject treated in each respective portion of the study, and last subject's end of study will be presented.

In phase 3, the number and percent of subjects randomized (enrolled) will be tabulated by the randomization stratification factors overall and by randomized treatment.

